7.2 General Study Procedures

Refer to the Schedule of Assessments (Table 5) for an outline of the procedures required at each study visit. The investigator at each site is responsible for ensuring that all study procedures are performed as specified in the protocol.

Each subject or their legally authorised representative must personally sign and date the Amgen- / IEC-approved informed consent form (ICF) before any study-specific procedures are performed. The ICF may be reviewed and signed/dated within 8 weeks of the screening assessments.

Demographic data collection including sex, date of birth, age, race, and ethnicity will be collected in order to study their possible association with subject safety data.

Each study visit may occur over a 2 consecutive day period. Study assessments including local laboratory Hb testing may be performed up to 1 day prior to the day of IP administration. For each study visit, all study procedures should be performed prior to IP administration.

7.2.1 Medical History

The Investigator or designee will collect a targeted medical history on the following: diabetes, hypertension (HTN), cerebrovascular accident (CVA), transient ischemic attack (TIA), peripheral vascular disease (PVD), myocardial infarction (MI), coronary artery, disease (CAD), congestive heart failure (CHF), cardiac arrhythmia, thromboembolic event, autoimmune disease, endocarditis, chronic obstructive pulmonary disease (COPD), pulmonary fibrosis, gastrointestinal bleeding, cholecystolithiasis (gall stones), pancreatitis, hepatitis, haemochromatosis, cirrhosis, urolithiasis (kidney stones), other vascular disease. Record all findings on the medical history eCRF. Adverse events that are ongoing at the end of the 20090160 study will not be reported as medical history, but will be carried forward as ongoing on the 20130113 study adverse event eCRF.

7.2.2 Physical Examination

A complete physical examination will be performed on all subjects during screening (a complete physical examination performed within 21 days prior to the start of screening may be used).

7.2.3 Physical Measurements

Height in centimeters and weight in kilograms should be measured without shoes. Height will be collected as part of screening assessments. Weight will be collected at every study visit.

The following measurements must be performed: systolic/diastolic blood pressure, heart rate, and temperature at every study visit. Subject should be in a supine position in a rested and calm state for at least 5 minutes before blood pressure assessments are conducted. The position selected for a subject should be the same that is used throughout the study and documented on the vital signs eCRF.

7.2.5 Thrombovascular Events

All subjects will be monitored closely at each visit for clinical signs and symptoms of thrombovascular events (TVEs):

- Arterial thromboembolic events [ATEs]:
 - stroke;
 - transient ischemic attack [TIA];
 - acute coronary syndromes [ACS]; and
 - other arterial thrombosis/embolism; and
- Venous thromboembolic events [VTEs]:
 - deep vein thrombosis [DVT];
 - pulmonary embolism [PE]); and
 - other venous thrombosis (excluding superficial venous thrombosis).

If any signs or symptoms are present, the subject will undergo specific laboratory and medical imaging studies to confirm TVEs. The medical imaging study or studies selected will depend on the anatomic site of the suspected TVE or organ of involvement (eg, Doppler ultrasound, venography, ventilation perfusion lung scan, angiography, magnetic resonance imaging [MRI]). If a TVE is confirmed, appropriate medical care according to standard local clinical practice should be initiated immediately and the TVE will be recorded in the eCRF.

7.2.6 Concomitant Medication and Red Blood Cell Transfusion

Key concomitant medications and RBC transfusion details will be collected from screening to the EOS visit. Concomitant medications include, but are not limited to, the use of any ESA or non-protocol specified dose of IP, haematopoietic growth factors, iron supplements, anti-hypertensive agents, anticoagulation therapies, and biological response modifiers (eg, thalidomide, lenalidomide, arsenic trioxide, azacitidine, decitabine.

Page 34 of 66

| Product: Darbepoetin alfa | |
|---------------------------|---------------|
| Protocol Number: 20130113 | |
| Date: 15 April 2013 | Page 35 of 66 |

The date of transfusion and number of units and volume, reason for transfusion, the associated pre-transfusion Hb value, and any associated AEs will be recorded in the eCRF.

7.2.7 Adverse Events Reporting

Adverse events that occur beginning on day 1 through the EOS visit will be reported using the applicable eCRF. All serious adverse events occurring from the date the subject signs the ICF through 30 days after the last dose of IP will be reported to Amgen.

Adverse events ongoing at the end of the parent study (20090160) will be carried forward to the eCRF of this study.

Refer to Section 9.2 for more detail on adverse events reporting.

7.2.8 Screening and Enrollment

The following procedures are to be completed during the screening period as noted in the Schedule of Assessments (Table 5):

- Confirmation that the Informed Consent Form has been signed
- Registration in IVR system
- Physical examination
- Physical measurements (height and weight)
- Demographic data including sex, date of birth, race, and ethnicity
- Complete medical history
- Heart rate, temperature, blood pressure
- Adverse event reporting
- Key concomitant medications and RBC transfusion history
- Local laboratory Hb assessment (if applicable)
- IP box number assignment in IVRS (if applicable)
- IP dose administration (if applicable)

Screening assessment, enrollment, and the day of first dose of IP may occur on the same day provided that the subject meets all eligibility criteria prior to IP dosing. The day of first dose may occur up to 10 days after the screening visit to accommodate scheduling. Local laboratory Hb results must be available and reviewed prior to each IP dose administration.

7.2.9 Treatment

Treatment begins when the first dose of protocol-required therapies is administered to a subject. The following procedures will be completed during the treatment period at the

times designated in the Schedule of Assessments (Table 5). Administration of IP will occur after completion of all study specific assessments as shown below:

- Weight
- Heart rate, temperature, blood pressure
- Adverse event reporting
- Key concomitant medications and RBC transfusion history
- Local laboratory Hb assessment
- IP box number assignment in IVRS
- IP dose administration

Subjects that end darbepoetin alfa treatment early will complete an EOS visit 3 weeks

± 7 days after last dose of darbepoetin alfa (Section 7.2.10).

7.2.10 End of Study Visit

- Weight
- Heart rate, temperature, blood pressure
- Adverse event reporting
- Key concomitant medications and RBC transfusion history
- Anti-darbepoetin alfa antibody specimen collection
- Registration of EOS visit in IVRS

7.3 Antibody Testing Procedures

Blood samples for antibody testing are to be collected on day 1 (prior to darbepoetin alfa dosing) and at the EOS visit for the measurement of anti-darbepoetin alfa binding antibodies. A Day 1 antibody sample is not required if the antibody specimen was appropriately collected in the MDS 20090160 study at the EOATP visit.

Samples testing positive for binding antibodies will also be tested for neutralizing antibodies and may be further characterized for quantity/titer, isotype, affinity and presence of immune complexes. Additional blood samples may be obtained to rule out anti-darbepoetin alfa antibodies during the study.

Sites will be notified of any positive neutralizing antibody results to darbepoetin alfa. If results are not provided, no neutralizing antibodies to darbepoetin alfa have been detected.

Subjects who test positive for neutralizing antibodies to darbepoetin alfa at the final scheduled study visit will be asked to return for additional follow-up testing. This testing

Page 37 of 66

is to occur approximately every 3 months starting from when the site has been notified of the positive result, until: (1) neutralizing antibodies are no longer detectable or (2) the subject has been followed for a period of at least 1 year (± 4 weeks) post administration of darbepoetin alfa. All follow-up results, both positive and negative will be communicated to the sites. More frequent testing (eg, every month) or testing for a longer period of time may be requested in the event of safety-related concerns.

Subjects who test positive for binding, non-neutralizing antibodies and have clinical sequelae that are considered potentially related to an anti-darbepoetin alfa antibody response may also be asked to return for additional follow-up testing.

8. WITHDRAWAL FROM TREATMENT, PROCEDURES, AND STUDY 8.1 Subject's Decision to Withdraw

Subjects have the right to withdraw from the study at any time and for any reason without prejudice to their future medical care by the physician or at the institution.

Subjects (or a legally acceptable representative) can decline to continue receiving investigational product and/or other protocol-required therapies or procedures at any time during the study but continue participation in the study. If this occurs, the investigator is to discuss with the subject the appropriate processes for discontinuation from investigational product and must discuss with the subject the options for continuation of the Schedule of Assessments (Table 5) and collection of data, including endpoints and adverse events. The investigator must document the change to the Schedule of Assessments (Table 5) and the level of follow-up that is agreed to by the subject (eg, in person, by telephone/mail, through family/friends, in correspondence/communication with other physicians, from review of the medical records).

Withdrawal of consent for a study means that the subject does not wish to receive further protocol-required therapies or procedures, and the subject does not wish to or is unable to continue further study participation. Subject data up to withdrawal of consent will be included in the analysis of the study, and where permitted, publically available data can be included after withdrawal of consent. The investigator is to discuss with the subject appropriate procedures for withdrawal from the study.

8.2 Investigator or Sponsor Decision to Withdraw or Terminate Subject's Participation Prior to Study Completion

The investigator and/or sponsor can decide to withdraw a subject from IP, protocol

procedures, or the study as a whole at any time prior to study completion.

8.2.1 Reasons for Removal From IP Treatment

Reasons for removal from protocol-required IP include any of the following:

- subject request
- safety concern (eg, due to an adverse event, ineligibility determined, protocol deviation, non-compliance, protocol-specified criteria (see Section 6.2.1.2 and Section 6.4.3), pregnancy)
- decision by sponsor (other than subject request or safety concern)
- death
- lost to follow-up
- decision by Sponsor (other than subject request, safety concern, lost to followup)

8.2.2 Reasons for Removal From the Study

Reasons for removal of a subject from the study are:

- decision by Sponsor
- withdraw of consent from study
- death
- lost to follow-up
- safety concern (eg, due to an adverse event, ineligibility determined, protocol deviation, non-compliance, protocol-specified criteria (see Section 6.2.1.2 and Section 6.4.3), pregnancy)

9. SAFETY DATA COLLECTION, RECORDING, AND REPORTING

9.1 Adverse Events

9.1.1 Definition of Adverse Events

An adverse event is defined as any untoward medical occurrence in a clinical trial subject. The event does not necessarily have a causal relationship with study treatment. The investigator is responsible for ensuring that any adverse events observed by the investigator or reported by the subject are recorded in the subject's medical record.

The definition of adverse events includes worsening of a pre-existing medical condition. Worsening indicates that the pre-existing medical condition (eg, diabetes, migraine headaches, gout) has increased in severity, frequency, and/or duration, and/or has an association with a significantly worse outcome. A pre-existing condition that has not

Page 39 of 66

worsened during the study or involves an intervention such as elective cosmetic surgery or a medical procedure while on study, is not considered an adverse event.

For situations when an adverse event or serious adverse event is due to MDS, report all known signs and symptoms. Death due to disease progression in the absence of signs and symptoms should be reported as the primary tumor type (eg, metastatic pancreatic cancer). Note: the term "disease progression" should not be used to describe the adverse event.

The investigator's clinical judgment is used to determine whether a subject is to be removed from treatment due to an adverse event. In the event a subject, or subject's legally acceptable representative requests to withdraw from protocol-required therapies or the study due to an adverse event, refer to Section 8.1 for additional instructions on the procedures recommended for safe withdrawal from protocol-required therapies or the study.

9.1.2 Definition of Serious Adverse Events

A serious adverse event is defined as an adverse event that meets at least one of the following serious criteria:

- fatal
- life threatening (places the subject at immediate risk of death)
- requires in-patient hospitalization or prolongation of existing hospitalization
- · results in persistent or significant disability/incapacity
- congenital anomaly/birth defect
- · other medically important serious event

An adverse event would meet the criterion of "requires hospitalization", if the event necessitated an admission to a health care facility (eg, overnight stay).

If an investigator considers an event to be clinically important, but it does not meet any of the serious criteria, the event could be classified as a serious adverse event under the criterion of "other medically important serious event". Examples of such events could include allergic bronchospasm, convulsions, blood dyscrasias, drug-induced liver injury, or events that necessitate an emergency room visit, outpatient surgery, or urgent intervention.

AMGEN

Page 40 of 66

| Product: Darbepoetin alfa | |
|---------------------------|--|
| Protocol Number: 20130113 | |
| Date: 15 April 2013 | |

9.2 Reporting of Adverse Events

9.2.1 Reporting Procedures for Adverse Events That Do Not Meet Serious Criteria

The investigator is responsible for ensuring that all adverse events observed by the investigator or reported by the subject that occur beginning on day 1 visit through the EOS are reported using the applicable eCRF (eg, Adverse Event Summary). Adverse events that are ongoing at the end of the MDS 20090160 will be transferred to the applicable adverse event eCRF.

The investigator must assign the following adverse event attributes:

- Adverse event diagnosis or syndrome(s), if known (if not known, signs or symptoms),
- Dates of onset and resolution (if resolved),
- Severity [and/or toxicity per protocol],
- Assessment of relatedness to IP, and
- Action taken.

The adverse event grading scale used will be the Common Terminology Criteria for Adverse Events (CTCAE). The grading scale used in this study is described in Appendix A. The investigator must assess whether the adverse event is possibly related to IP. This relationship is indicated by a "yes" or "no" response to the question: Is there a reasonable possibility that the event may have been caused by the IP?

The criteria for grade 4 in the CTCAE grading scale differs from the regulatory criteria for serious adverse events. It is left to the investigator's judgment to report these grade 4 abnormalities as serious adverse events.

If the severity of an adverse event changes from the date of onset to the date of resolution, record a single event for each level of severity on the Adverse Event Summary eCRF.

The investigator is responsible for reviewing laboratory test results and determining whether an abnormal value in an individual study subject represents a clinically significant change from the subject's baseline values. In general, abnormal laboratory findings without clinical significance (based on the investigator's judgment) are not to be recorded as adverse events. However, laboratory value changes that require treatment or adjustment in current therapy are considered adverse events. Where applicable, clinical sequelae (not the laboratory abnormality) are to be recorded as the adverse event.

The Investigator is expected to follow reported adverse events until stabilization or reversibility.

9.2.2 Reporting Procedures for Serious Adverse Events

The investigator is responsible for ensuring that all serious adverse events observed by the investigator or reported by the subject that occur after signing of the informed consent through 30 days after the last dose of IP are to be recorded in the subject's medical record and are submitted to Amgen. The serious adverse event must be submitted to Amgen within 24 hours following the investigator's knowledge of the event via the applicable eCRF.

After the protocol-required reporting period defined above, the investigator does not need to actively monitor subjects for serious adverse events. However, if the investigator becomes aware of a serious adverse event after this protocol-required reporting period, the investigator will report the event to Amgen within 24 hours following the investigator's knowledge of the event. SAEs reported outside of the protocol-required reporting period will be captured within the safety database as clinical trial cases for the purposes of expedited reporting.

If the electronic data capture (EDC) system is unavailable to the site staff to report the Serious Adverse Event, the information is to be reported to Amgen via an electronic Serious Adverse Event (eSAE) Contingency Report Form within 24 hours of the investigator's knowledge of the event. See Appendix B for a sample of the Serious Adverse Event Worksheet/electronic Serious Adverse Event Contingency Report Form. For EDC studies where the first notification of a Serious Adverse Event is reported to Amgen via the eSerious Adverse Event Contingency Report Form, the data must be entered into the EDC system when the system is again available.

In addition to the attributes listed in Section 9.2.1, the investigator must also complete the Serious Adverse Event section of the Adverse Event Summary eCRF.

The investigator must assess whether the serious adverse event is possibly related to any study mandated activity or procedure. This relationship is indicated by a "yes" or "no" response to the question: "Is there a reasonable possibility that the SAE may have been caused by a study activity/procedure"?

The investigator is expected to follow reported serious adverse events until stabilization or reversibility.

Page 42 of 66

New information relating to a previously reported serious adverse event must be submitted to Amgen. All new information for serious adverse events must be sent to Amgen within 24 hours following knowledge of the new information. The investigator may be asked to provide additional follow-up information, which may include a discharge summary or extracts from the medical record. Information provided about the serious adverse event must be consistent with that recorded on the applicable eCRF (eg, Adverse Event Summary eCRF).

If a subject is permanently withdrawn from protocol-required therapies because of a serious adverse event, this information must be submitted to Amgen.

Amgen will report serious adverse events and/or suspected unexpected serious adverse reactions as required to regulatory authorities, investigators/institutions, and IECs in compliance with all reporting requirements according to local regulations and good clinical practice.

The investigator is to notify the appropriate IEC of serious adverse events occurring at the site and other adverse event reports received from Amgen, in accordance with local procedures and statutes.

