6.2.1.2 Dosage Adjustments, Delays, Rules for Withholding or Restarting, Permanent Discontinuation

There will be no interactive voice recognition system (IVRS) guidance for IP dosing in this protocol. The IVRS will only be used in this study to track IP supply to sites and will allocate a IP box number based on the IP dose information entered by the site.

Each subject entering the study will continue the last IP dose and frequency from the parent study (20090160). The investigator may choose to increase the dose of darbepoetin alfa with the maximum dose permitted of 500 µg Q2W. Dose increases should follow a step-wise approach, (eg, 300 µg to 500 µg; 200 µg to 300 µg) with at least 8 weeks at a given dose before the dose may be increased.

The frequency of darbepoetin alfa administration may also be changed, eg, from Q2W to Q3W dosing. No two Q3W or Q2W doses should be administered within any contiguous 14-day or 7-day period, respectively.

The Investigators should use their clinical judgment to assess the best dose and frequency considering risks and benefits, and subject needs. Adjustments to the darbepoetin alfa dose should be made based on the most recent local hemoglobin (Hb) value obtained within 1 day before the dosing visit. Dosing information and local Hb values will be recorded in the eCRF. The reason for a dose change is to be recorded on the eCRF.

Investigators should closely monitor each subjects' Hb values and suspend the dose of IP when the Hb exceeds the 12 g/dL threshold. IP should temporarily be withheld until Hb falls to ≤ 11.0 g/dL at which time IP may be restarted at a dose that is reduced from the previous dose (ie, 500 µg to 300 µg; 300 µg to 200 µg; 200 µg to 100 µg. Table 4 provides an outline of the recommended dose reductions.

Subjects will be permanently discontinued from darbepoetin alfa treatment and will complete the EOS visit at the next scheduled study visit if at any time the:

- subject loses erythroid response defined as Hb decrease of ≥ 1 g/dL compared to day 1 (Hb averaged over 8 weeks)
- subject becomes transfusion dependent defined as ≥ 4 units of RBC transfusion relative to previous 8 weeks prior to enrolment

| Dose | No Previous Dose Reduction | 1 Previous Dose Reduction | 2 Previous Dose Reductions | 3 Previous Dose Reductions |
|---------------|--|--|--|----------------------------------|

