7. STUDY PROCEDURES

7.1 Schedule of Assessments

| | Screen / Enroll | Active Treatment Period | End of Study ^g |
|--|---------------------------------|---|------------------------------|
| Study Week | 72 / 73 ^a / Day 1 | Q3W or Q2W dosing up to week 73 (Q3W) | 76 |
| Informed Consent | x | | |
| Medical history | x | | |
| Physical examination | x | | |
| Physical measurements (height and weight) ^b | x | performed at each visit | x |
| Vital Signs (heart rate, temperature, blood pressure) | х | performed at each visit | x |
| Assess for signs and symptoms of clinically relevant TVE | x | performed at each visit | x |
| Adverse Events (AEs), Serious Adverse Events (SAEs) ^C | x | performed at each visit | x |
| Key concominant medications, and red blood cell (RBC) transfusions | x | Assessed at each visit and throughout the study | |
| Local laboratory haemoglobin for dosing decision | x | performed at each visit | |
| IP (darbepoetin alfa) administration ^e | х | performed at each visit | |
| Darbepoetin alfa antibody sample collection | x ^f | | х |

Table 5. Schedule of Assessments

a. Last visit of the MDS 20090160 study at week 72 / 73 is the first dosing visit for 20130113.

b. Height only collected as part of screening. Weight collected at each visit.

c. AEs and SAEs will be reported throughout the study through 30 days after last dose of IP (darbepoetin alfa).

d. Dosing will occur Q3W ± 6 day or Q2W ± 6 days. No 2 Q3W or Q2W doses should be administered within any contiguous 14-day or 7-day period, respectively. Dosing decision based on local lab Hb taken within 1 day before IP dosing visit (See Protocol Section 6.2.1.2 for dosing guidelines).

e. Results of local laboratory Hb must be available and reviewed prior to IP adminstration.

f. A Day 1 antibody sample is not required if appropriately collected in the MDS 20090160 study at the End of the Active Treatment Period (EOATP) visit.

g. End of Study (EOS) visit at week 76 or 3 weeks after last dose of IP from Q3W or Q2W dosing for subjects that end IP early.

Page 33

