2.1 Definitions

Progression to Acute Myelogenous Leukemia (AML)

Progression to AML in this study will be assessed according to World Health Organization (WHO) guidelines (peripheral or blast cells \geq 20%, presence of pathognomonic AML cytogenetic change, or evidence of marrow blast criteria for erythroleukemia).

Red Blood Cell (RBC) Transfusions

This is defined as any RBC transfusion (includes packed RBCs or whole blood and excludes platelets) given during an assessment period, regardless of hemoglobin concentration level at the time of transfusion or reason for transfusion. Subjects with at least 1 RBC transfusion during the assessment period will be considered “transfused”. Subjects with no RBC transfusions during the assessment period will be considered “not transfused”.

Treatment-emergent Adverse Event

A treatment-emergent adverse event (AE) is any event reported via the AE summary case report form (CRF) with an onset date between study day 1 and EOS.

- A treatment-emergent serious adverse event (SAE) is any event reported with an onset date between the date the subject signs the Informed Consent Form (ICF) through 30 days after the last dose of IP.
- Day 1 / week 1 dosing visit is expected to align with the end of the active treatment period (EOATP) visit of the MDS 20090160 study (window +10 days)
- End of Study visit performed 3 weeks \pm 7 days after last dose of IP.

Thrombovascular event (TVE)

Thrombovascular events are adverse events that include arterial thromboembolic events (ATEs) and venous thromboembolic events (VTEs). These events will be coded using MedDRA version 17 (or higher) and identified using a Standardized MedDRA Query (SMQ 20000081, “embolic and thrombotic events” excluding terms from the sub-SMQ 20000083, “embolic and thrombotic events, vessel type unspecified and mixed arterial and venous”) or more appropriate query available at the time of analysis. ATEs and VTEs are described below:

- **Arterial thromboembolic event (ATE)**
ATEs include stroke, transient ischemic attack (TIA), acute coronary syndromes (ACS), and other arterial thrombosis/embolism. These events will be coded using MedDRA version 17 (or higher) and identified using the sub-SMQ 20000082 (“embolic and thrombotic events, arterial”) or more appropriate query available at the time of analysis.
- **Venous thromboembolic event (VTE)**

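### The SAE window closes 30 days after the last dose even if the subject is still on study in an Hb hold, so for later onsets inclusion depends on whether dosing resumes

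*Protocol*

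**What the plan says.** Three places tie the end of the SAE window to the last dose.

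- Protocol 7.2.7: "All serious adverse events occurring from the date the subject signs the ICF through 30 days after the last dose of IP will be reported".
- Protocol 9.2.2: SAEs "that occur after signing of the informed consent through 30 days after the last dose of IP are to be recorded" and submitted. Once that period is over, "the investigator does not need to actively monitor subjects for serious adverse events". A later SAE that comes to the investigator's notice must still be sent within 24 hours, and it is held in the safety database to support expedited reporting.
- SAP 2.1: a treatment-emergent SAE has an "onset date between the date the subject signs the Informed Consent Form (ICF) through 30 days after the last dose of IP".

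Neither document says what the last dose is for a subject whose treatment is temporarily on hold. Protocol 6.2.1.2 suspends dosing when Hb exceeds 12 g/dL and continues: "IP should temporarily be withheld until Hb falls to ≤ 11.0 g/dL at which time IP may be restarted". It gives no maximum length for the hold. The only outer limit is that no dosing takes place after week 73 (Study Glossary).

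Other adverse events follow a different clock. Protocol 7.2.7 and 9.2.1 collect them from day 1 to the end-of-study (EOS) visit, and the general treatment-emergent definition in SAP 2.1 runs from study day 1 to EOS. Table 5 schedules both AE and SAE assessment at every visit. Its footnote c describes reporting as lasting for the whole study and also as ending 30 days after the last dose. For a subject in a long hold, those two descriptions differ.

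**The concern.** A 30-day tail after the last dose works when treatment stops for good and EOS follows about three weeks later. It works less well when dosing is paused and the subject remains on study, because nobody knows at the time whether the pre-hold dose will prove to be the last one. That is settled only later, by whether dosing resumes.

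For an SAE that starts more than 30 days after the pre-hold dose, the event can itself settle the matter. Death rules out restart. After a thromboembolic event, 6.2.1.2 recommends withdrawal from treatment. In those cases the pre-hold dose becomes the last dose and the SAE falls outside the window. The same type of event, followed by a restart, falls inside it. A non-serious event on the same day is collected either way, provided EOS has not occurred.

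The study's stated purpose includes describing the safety of longer-term use. A rule that fixes SAE status by the consequence of the event is undesirable in such a study, even if few subjects are affected.

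**Working it through.** The study is descriptive and gives no sample size or power figure to reproduce. The check is date arithmetic on the documents' own rules.

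**Inputs**
- SAE cut-off: last dose + 30 days (Protocol 7.2.7, 9.2.2; SAP 2.1).
- Dosing interval: "Dosing will occur Q3W ± 6 day or Q2W ± 6 days" (Table 5 footnote d), so *v* = 21 or 14 days.
- Length of hold: no maximum stated (6.2.1.2).
- EOS after early end of treatment: 3 weeks ± 7 days after the last dose (Protocol 7.2.9; SAP 2.1).

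**Assumptions.** Day 0 is the last dose before the hold, and dosing can resume only at a scheduled visit.

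**Step 1: days outside the window.** After *k* withheld doses, the next visit at which dosing could resume is day *v*(*k* + 1). If dosing never resumes, the days outside the window up to that visit are max(0, *v*(*k* + 1) − 30). The last column moves that one visit by the 6-day tolerance.

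| Schedule | Doses withheld | Next visit (day) | Days outside, nominal | Days outside, visit ± 6 days |
|---|---|---|---|---|
| Q3W | 1 | 21 × 2 = 42 | 42 − 30 = 12 | 6 to 18 |
| Q3W | 2 | 21 × 3 = 63 | 63 − 30 = 33 | 27 to 39 |
| Q2W | 1 | 14 × 2 = 28 | 0 | 0 to 4 |
| Q2W | 2 | 14 × 3 = 42 | 42 − 30 = 12 | 6 to 18 |

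On Q3W, the first withheld dose falls on day 21 and leaves 30 − 21 = 9 days of window.

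**Step 2: the same onset, with and without restart.** An SAE on day *t* is inside the window if *t* ≤ (last dose actually given) + 30. Suppose that any restart is on day 63, which moves the cut-off to 63 + 30 = 93.

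| SAE onset | Dosing never resumes (cut-off day 30) | Dosing resumes on day 63 (cut-off day 93) |
|---|---|---|
| Day 20 | inside | inside |
| Day 30 | inside | inside |
| Day 31 | outside by 1 day | inside |
| Day 45 | outside by 15 days | inside |

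Only onsets after day 30 change status.

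**Step 3: outer bound.** With a last dose in week 1 and a hold lasting to week 73, the hold is 72 × 7 = 504 days, of which 504 − 30 = 474 lie outside the window. This is a limit set by the wording, not a likely case.

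**Step 4: does EOS timing close the gap?** Counted from the last dose, EOS falls on day 21 − 7 = 14 to day 21 + 7 = 28. Both are before day 30, and both have already passed for a subject held longer than that. A cut-off that uses this nominal EOS date would therefore still be day 30.

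**The case against.** The best defence is that the plan catches these events by other routes. Most of it stands.

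- **General treatment-emergent definition.** The day 1 to EOS definition in SAP 2.1 does not exclude serious events, and SAEs are entered on the same AE summary form. A serious event before EOS can therefore count in the primary endpoint. The 30-day SAE bullet can be read as an addition to that definition and not as a limit on it.
- **Visits continue.** Table 5 requires SAE assessment at each visit. An investigator who is seeing the subject would normally learn of the event, and 9.2.2 then requires it to be sent within 24 hours.
- **Other outputs.** SAP 5 plans listings of fatal events, events leading to withdrawal from treatment, and thrombovascular events, none with a stated 30-day limit. Section 9.2.2 also requires the sponsor to be told when an SAE leads to permanent withdrawal, with no time limit.

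A reader might infer that SAEs which end treatment are dropped in general. The documents do not support that: any onset up to day 30 is inside the window, whatever its consequence. A reader might also infer that late SAEs go unreported or leave the primary endpoint. The three routes above contradict that.

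The defence does not remove two stated rules. Section 9.2.2 lifts active SAE monitoring once the window closes, which is at odds with Table 5 for a subject still attending visits. The treatment-emergent SAE definition in the SAP excludes the event by its date. The SAE listing in SAP 5 does not say which window governs it.

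**Conclusion.** The point holds within limits. For a held subject still on study, an SAE starting more than 30 days after the pre-hold dose has its SAE status decided afterwards, by whether dosing resumes. If the event prevents restart, the loss is required active ascertainment, classification as a treatment-emergent SAE, and possibly a place in the SAE listing. The event is not hidden from the sponsor and can still appear as a general treatment-emergent event.

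On nominal visits, the uncovered period is 12 days after one withheld Q3W dose and 33 after two. On Q2W it is none after one and 12 after two. These figures assume restart at scheduled visits only.

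The documents give no hold rate and no SAE rate, so no expected number of affected events can be stated. It may be tempting to express one event as a percentage of subjects. That would need an assumed denominator, because SAP 4.1.2 says only that fewer than 10 subjects are projected, and it plans listings with no summary statistics. The effect is on the status of individual listed events. The wording is worth correcting because the change is small and removes a dependence on outcome.

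**What to change.** 1. In Protocol 7.2.7, 9.2.2 and Table 5 footnote c, and in the SAE bullet of SAP 2.1, close the SAE window at the later of (a) the subject's actual end of study, meaning the EOS visit as performed, withdrawal from the study, or death, and (b) 30 days after the last dose of IP. The Study Glossary already defines a subject's end of study by these three events. The actual date is needed because a subject who dies has no EOS visit, and because the nominal EOS date would leave the cut-off at day 30 (Step 4).
2. Make the sentence in 9.2.2 that lifts active SAE monitoring apply only after that point.
3. Reconcile EOS timing for held subjects who never restart. Protocol 6.2.1.2 gives both the next scheduled visit (for specified discontinuations) and about three weeks after the last IP dosing visit. Table 5 footnote g, Protocol 7.2.9 and SAP 2.1 count three weeks from the last dose.
4. State in SAP 5 which window governs the SAE listing.

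No dose, hold or restart rule changes. The cost is one clause in four places, a few consequential edits, and possibly a few more SAE records.
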